4.2.2.3 Management of mucositis/stomatitis

General and grade specific recommendations are described in [Table 4.2.2.3:1](#). For dose adjustment refer to [Section 4.1.4](#) and for restrictions on concomitant therapies refer to Sections [4.2.3](#), [10.5](#) and [10.6](#).

Mucositis and associated pain may lead to fluid loss and hypo-alimentation. Therefore maintaining fluid balance and appropriate pain control are crucial. Please assure that parents are alerted to this and describe early signs and symptoms of mucositis and fluid loss clearly to caregivers/patients. Caregivers/patients should quickly seek medical advice on occurrence of initial signs and symptoms. In addition below measures may be useful.

Treatment is supportive and aimed at symptom control. These may include atraumatic cleansing and rinsing with non-alcoholic solutions such as normal saline, diluted salt and baking soda solution (e.g. one-half teaspoonful of salt and one teaspoon of baking soda in one quart of water every four hours); avoidance of agents containing iodine, thyme derivatives and prolonged use of hydrogen peroxide; dietary manoeuvres such as promotion of soft, non-irritating foods like ice-creams/sorbet as tolerated, mashed/cooked vegetables, potatoes and avoidance of spicy, acidic or irritating foods such as peppers, curries, chillies, nuts and alcohol. If the patient is unable to swallow foods or liquids, parenteral fluid and/or nutritional

Proprietary confidential information.

© 2017 Boehringer Ingelheim International GmbH or one or more of its affiliated companies. All rights reserved.

This document may not - in full or in part - be passed on, reproduced, published or otherwise used without prior written permission.

support may be needed. Examples of some of the agents suggested in [Table 4.2.2.3:1](#) include: topical analgesics –viscous lidocaine 2%; mucosal coating agents - topical kaolin/pectin; oral antacids, maltodextrin, sucralfate; topical antifungals – nystatin suspension. (Adapted from [P11-09424](#))

Table 4.2.2.3: 1 Grade specific treatment recommendations of study-drug related mucositis/stomatitis

Severity (CTCAE grading)	Description	Treatment recommendations*	Intervention concerning afatinib treatment/ dose modification
Mild (Grade 1)	Minimal symptoms; normal diet	Oral rinses with agents such as non-alcoholic mouth wash, normal saline, diluted salt and baking soda solution.	No change.
Moderate (Grade 2)	Symptomatic, but can eat and swallow modified diet	Addition of topical analgesic mouth treatments, topical corticosteroids, antiviral therapy if herpetic infection confirmed, antifungal therapy preferably topical on a case by case basis.	Maintain dose if tolerable; Hold dose if intolerable until recovery to grade ≤ 1 , then restart at the same dose.
Severe (Grade 3)	Symptomatic and unable to adequately aliment or hydrate orally	Same as for Grade 2; institute additional symptomatic therapy (topical or systemic) as clinically indicated.	Hold dose until recovery to grade ≤ 1 or baseline, then restart at the reduced dose according to Section 4.1.4 .
Life threatening (Grade 4)	Symptoms associated with life-threatening consequences	Same as for Grade 2; institute additional symptomatic therapy (topical or systemic) as clinically indicated.	Hold dose until recovery to grade ≤ 1 or baseline, then restart at the reduced dose according to Section 4.1.4

*Also consider Rugo et al. ([R17-1688](#))

4.2.3 Restrictions

4.2.3.1 Restrictions regarding concomitant treatment

Concomitant medications, or therapy to provide adequate supportive care, may be given as clinically necessary.

Palliative radiotherapy may be given as described in [Section 4.2.1](#).

Additional experimental anti-cancer treatment and/or standard chemo-, immunotherapy, hormone treatment, or radiotherapy (other than palliative radiotherapy for symptom control) is not allowed concomitantly with the administration of study treatment.

Afatinib is a substrate of the P-gp transporter. Caution should be exercised when combining afatinib with strong P-gp modulators including, but not limited to strong P-gp inhibitors ritanovir, cyclosporine A, ketoconazole, itraconazole, erythromycin, verapamil, quinidine, tacrolimus, nelfinavir, saquinavir, and amiodarone. Conversely, strong P-gp inducers such as rifampicin, carbamazepine, phenytoin, phenobarbital or St. John's Wort may decrease the plasma concentrations of afatinib. Co-administration of P-gp modulators must be avoided

Proprietary confidential information.

© 2017 Boehringer Ingelheim International GmbH or one or more of its affiliated companies. All rights reserved.

This document may not - in full or in part - be passed on, reproduced, published or otherwise used without prior written permission.

during course 1 of Phase I dose finding. In addition P-gp modulators should be avoided within 14 days or at least 5 half-lives of the drug (whichever is longer) prior to the first dose of afatinib. For use of strong P-gp inhibitors after course 1 of the dose finding part and during the MTD expansion cohort, staggered dosing must be considered. For use of strong P-gp inducers after course 1 of the dose finding part and during the MTD expansion cohorts/Phase II part, afatinib daily dose should be increased based on tolerability and discussion with the sponsor. For a list of potent P-gp inhibitors and inducers see [Appendix 10.4](#).

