 - 13 Imaging (CT or MRI for CNS tumours or soft tissue lesions) assessment is to be performed every 8 weeks until progression of disease. In case of objective response, the latter has to be confirmed 4 to 6 weeks after initial OR observation. Consecutive imaging assessment will be performed every 8 weeks. In exceptional cases when patients have been stable on treatment for at least 2 consecutive images (i.e. 16 weeks), imaging intervals may be extended to 12 weeks upon discussion between the investigator and the sponsor.
 - 14 Tumour marker(s) in urine or blood as indicated depending on tumour type (e.g. catecholamines (VMA/HVA, dopamine), NSE in neuroblastoma)
 - 15 Intra-patient dose escalation might be allowed as soon as the next higher dose tier is completed and considered safe (applicable to dose finding part only). A dose reduction can also be applied in case of drug-related toxicity (see [Section 4.1.4.3](#))
 - 16 New kit(s) of trial drug must be dispensed at visit 1 of each course. If needed (e.g. in case a dose adaptation has to be applied during treatment course), new kit(s) of trial drug might be dispensed outside of the planned visit schedule
 - 17 A full PK profile (extensive PK sampling) is to be taken at course 1, day 1: pre-dose before afatinib administration then 1h, 2h, 3h, 4h, 5h, 6h, 8h and 24h after administration and to be repeated at steady state on day8. In exceptional cases where extensive PK sampling is not possible, a limited sampling approach must be applied with blood sampling before, 1h and 3 h after afatinib administration. An additional trough sample is to be taken on day 15 to confirm steady state exposure to afatinib. In addition, trough CSF sampling (from Rickham, Ommaya reservoirs or from lumbar puncture performed for clinical reasons not related to the trial) may be taken on day 8 or later. This CSF sampling is optional. Each trough CSF sample has to be accompanied by a trough plasma sample taken at the same time-point. For further details on time points and sampling volumes, see [Section 5.5.2](#) and [Appendix 10.3](#).
 - 18 During the dose escalation part, a DLT confirmation fax has to be sent to the sponsor before start of course 2.
 - 19 AE/SAE after the 28-30 days FU period have to be reported only if considered relevant by the investigator.
-
- 22 Lansky for patients ≤ 12 years or Karnofsky for patients older than 12 years at time of informed consent

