Afatinib is bound covalently to proteins to a variable extent and covalent protein adducts were the major circulating metabolites in the plasma. Afatinib did not show relevant inhibition or induction of cytochrome P450 isoenzymes, and it appears unlikely that drug-drug interactions based on this mechanism will occur.

Afatinib is a substrate of the P-gp transporter. Concomitant administration of the potent P-gp inhibitor ritonavir did not relevantly change the exposure to 40 mg afatinib when taken

Proprietary confidential information.

© 2017 Boehringer Ingelheim International GmbH or one or more of its affiliated companies. All rights reserved.

This document may not - in full or in part - be passed on, reproduced, published or otherwise used without prior written permission.

simultaneously with or 6 h after afatinib but increased the bioavailability of afatinib (single dose of 20 mg) by 48% and 39% for AUC_{0-∞} and C_{max} when given 1 h before afatinib, respectively. Pretreatment with the potent P-gp inducer rifampicin decreased the plasma exposure of 40 mg afatinib by 34 % (AUC_{0-∞}) and 22 % (C_{max}), respectively. Caution should be exercised when combining afatinib with potent P-gp modulators, for further information see [Appendix 10.4](#).

Afatinib exposure is expected to be comparable for the film-coated tablets and the capsule and solvent for oral solution (both formulations are to be used in this trial).

In pre-clinical studies afatinib is not irritant to intact skin but an ocular irritant. Afatinib is mutagenic in a single bacteria strain, but did not show genotoxic potential in vivo when tested up to overt toxic/lethal doses. Studies on embryo-foetal development in rats and rabbits up to life-threatening doses have revealed no indication of teratogenicity.

In adult cancer patients, the choice of the starting dose of 40 or 50 mg daily with afatinib monotherapy was based on the expected balance between patient's tolerability and the required level of target inhibition. A dose of 40 mg daily has been used in patients with NSCLC or HNSCC not previously exposed to EGFR-targeted treatments. A dose of 50 mg

Proprietary confidential information.

© 2017 Boehringer Ingelheim International GmbH or one or more of its affiliated companies. All rights reserved.

This document may not - in full or in part - be passed on, reproduced, published or otherwise used without prior written permission.

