4.1.4.3 Dose reduction of afatinib

Treatment related toxicities will be managed by treatment interruptions and subsequent dose reductions of afatinib according to the schedule described in [Table 4.1.4.3: 1](#). Dose reductions will apply to individual patients only. Once the treatment dose has been reduced, it cannot be increased later.

To prevent the development of more severe adverse events, treatment related diarrhoea, nausea and vomiting or rash should be managed early and proactively as described in [Section 4.2](#).

Proprietary confidential information.

© 2017 Boehringer Ingelheim International GmbH or one or more of its affiliated companies. All rights reserved.

This document may not - in full or in part - be passed on, reproduced, published or otherwise used without prior written permission.

Table 4.1.4.3:1 Dose reduction scheme for afatinib

AE type and CTCAE Grade	Action	Dose reduction scheme

Events related to study drug:
 
 • Diarrhoea Grade 2 persisting for 7 or more consecutive days despite adequate anti-diarrhoeal medication/hydration • Reduced renal function to \geq Grade 2 as measured by serum creatinine, proteinuria or decrease in glomerular filtration rate of more than 50% from baseline • Any drug related AE Grade \geq3 	
Pause treatment until patient has recovered to Grade \leq1 or baseline¹.
 
Resume treatment at reduced dose according to schedule opposite.
 
If patient has not recovered to Grade \leq1 or baseline¹ within 14 days, study treatment must be permanently discontinued².
	
If patient was treated at dose level 3, resume treatment at dose level 2
 
If patient was treated at dose level 2, resume treatment at dose level 1
 
If patient was treated at dose level 1, resume treatment at dose level 0
 
If patient was treated at dose level 0, resume treatment at dose level -1
 
If patient was treated at dose level -1, discontinue afatinib.

Acute onset and/or unexplained worsening of pulmonary symptoms (dyspnoea requiring supplementation of oxygen with cough and/or fever)
	
Pause afatinib while clinical assessment to exclude ILD is completed.
	
If ILD is ruled out as a cause of symptoms, grade symptoms and relatedness and report as AEs. If AEs are not related, resume afatinib at current dose.
 
If ILD is confirmed, discontinue afatinib.

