10.4 P-GLYCOPROTEIN INHIBITORS AND INDUCERS

Examples of P-gp modulators that can be considered as potent inhibitors and/or potent inducers of the P-gp (P-gp is also known as MDR1) are listed below in Table 10.4: 1.

Table 10.4: 1 List of potent inhibitors and inducers of P-glycoprotein (MDR1)

Inhibitors	Inducers
Amiodarone	Carbamazepine
Azithromycin	Phenytoin
Captopril	Rifampicin
Carvedilol	St John's wort
Clarithromycin	Phenobarbital salt
Conivaptan	Tipranavir
Cyclosporine	Ritonavir
Diltiazem	
Dronedarone	
Erythromycin	
Felodipine	
Itraconazole	
Ketoconazole	
Lopinavir	
Nelfinavir	
Ritonavir	
Quinidine	
Ranolazine	
Saquinavir	
Tacrolimus	
Ticagrelor	
Verapamil	

As the information on potent inhibitors and inducers of P-gp may evolve, it is important for the investigator to assess such status on concomitant therapies. Of note, co-administration of P-gp modulators must be avoided during course 1 of Phase I dose finding.

In addition P-gp modulators should be avoided within 14 days or at least 5 half-lives of the drug (whichever is longer) prior to the first dose of afatinib. For use of strong P-gp inhibitors after course 1 of the dose finding part and during the MTD expansion cohort, staggered dosing must be considered. For use of strong P-gp inducers after course 1 of the dose finding part and during the MTD expansion cohort, afatinib daily dose should be increased based on tolerability and discussion with the sponsor.

In case of questions the sponsor/sponsor representative should be contacted.

Proprietary confidential information.

© 2017 Boehringer Ingelheim International GmbH or one or more of its affiliated companies. All rights reserved.

This document may not - in full or in part - be passed on, reproduced, published or otherwise used without prior written permission.

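### The dosing instructions for P-gp inducers and for ritonavir conflict with other protocol passages and need reconciling

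*Protocol*

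**What the plan says.** **Inducers.** Protocol Section 4.2.3.1 states that "strong P-gp inducers such as rifampicin, carbamazepine, phenytoin, phenobarbital or St. John's Wort may decrease the plasma concentrations of afatinib". If such a drug is used after course 1 of dose finding, or in the expansion/Phase II part, the "afatinib daily dose should be increased based on tolerability and discussion with the sponsor". Appendix 10.4 repeats the instruction. Neither place gives the size of the increase.

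**Inhibitors.** The instruction here is different: "For use of strong P-gp inhibitors after course 1 of the dose finding part and during the MTD expansion cohort, staggered dosing must be considered".

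**After a reduction.** Section 4.1.4.3, which covers reductions for treatment-related toxicity, states: "Once the treatment dose has been reduced, it cannot be increased later".

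**Intra-patient escalation.** Flow chart footnote 15 allows it once the next tier is complete and "considered safe (applicable to dose finding part only"). Section 4.1.4.2 likewise describes it only for dose-finding patients.

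**Ritonavir.** Table 10.4:1 ("List of potent inhibitors and inducers of P-glycoprotein (MDR1") has ritonavir in both columns. Section 4.2.3.1 names it only among the "strong P-gp inhibitors ritanovir, cyclosporine A, ketoconazole" group (spelled that way in the text) and not among its inducer examples. Section 1.2 reports that ritonavir given 1 h before afatinib "increased the bioavailability of afatinib (single dose of 20 mg) by 48% and 39"% for AUC and Cmax respectively. Given together with afatinib or 6 h after it, ritonavir did not materially change exposure to a 40 mg dose.

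**SAP.** Table 6.2:1 makes an afatinib dose change outside the protocol an important deviation (code C1). It is assigned manually, and the table lists no analysis from which such a patient is excluded.

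**The concern.** A site that follows one section can breach another. A patient whose dose was cut for toxicity and who then starts a strong inducer is covered by one sentence directing an increase and another forbidding it. A patient on ritonavir can be sent to staggered dosing or to a dose increase, depending on which column of the table is read. For that drug the protocol's own data show afatinib exposure rising or unchanged, never falling.

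The first consequence is for patient safety. The second is for the record: C1 depends on knowing what the protocol permits, and for these increases it does not say clearly. Cohorts in the expansion part may be as small as five patients, and that part is meant to confirm a safe recommended Phase II dose, so uneven handling of even one patient would be visible in the cohort's dose and safety summaries.

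**Working it through.** No planned figure has to be reproduced. The check sets the passages side by side, with a short calculation to size the effect.

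1. *Increase against no re-increase.* Sections 4.2.3.1 and 10.4 direct an increase, subject to tolerability and sponsor discussion. Section 4.1.4.3 bars any increase after a reduction. Neither cross-refers to the other or states an exception. The overlap is a patient who is dose-reduced and later needs a strong inducer. The MTD is level 0 (Section 4.1.3), and Table 4.1.4.3:1 reduces level 0 to level -1. For an expansion patient started at level 0, the next tabulated step up is therefore the level at which the toxicity occurred.

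2. *Ritonavir.* One drug, two columns, two instructions. The introduction to Table 10.4:1 allows a drug to be an inhibitor, an inducer or both, so the double listing is not an error in itself. What is missing is a rule for which instruction then applies. The inducer listing also does not match Section 4.2.3.1 (inhibitor only) or Section 1.2 (exposure raised or unchanged).

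3. *Escalation limit.* Footnote 15 and Section 4.1.4.2 restrict intra-patient escalation to dose finding. Section 4.2.3.1 applies the inducer increase in the expansion part. Neither says whether the increase falls inside or outside the restriction. One monitor could code it C1 and another could treat it as compliant.

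4. *Size.* Inputs: level 0 is 80% of the adult dose (18 mg/m²) and level 1 is 100% (23 mg/m²), from Table 4.1.3:1; AUC falls 34% with rifampicin and rises 48% with ritonavir 1 h before, from Section 1.2. Two assumptions are made: exposure is proportional to dose, and the increase is one tier. The second is purely illustrative, because the protocol names no size.
   - Step from level 0 to level 1: 100/80 = 1.25, or 23/18 = 1.28.
   - Rifampicin-size effect at level 1, relative to level 0 without an inducer: (1 - 0.34) × 1.25 = 0.83, or 0.66 × 23/18 = 0.84.
   - Ritonavir 1 h before: 1.48 at level 0; 1.48 × 1.25 = 1.85 at level 1.

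   The same instruction partly offsets a fall in exposure in the first case and adds to a reported rise in the second. Section 1.2 describes exposure as slightly more than dose-proportional, so the true ratios after an increase would be somewhat higher. These figures show why the passages must agree; they are not a dosing proposal.

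**The case against.** The strongest reply is that the passages can be read together.

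- *Footnote 15 and Section 4.1.4.2* concern moving patients up a tier so that early cohorts are not under-dosed. An interaction rule that expressly names the expansion part can stand beside them. This largely holds, and a reader who infers that footnote 15 flatly prohibits the inducer increase goes further than the text. What remains is that the boundary is unwritten and C1 coding depends on it.
- *Section 4.1.4.3* deals with toxicity, and a patient already reduced for toxicity might be judged to fail the tolerability condition in Section 4.2.3.1. That is a possible reading, but the protocol does not state it, and the bar in Section 4.1.4.3 is unqualified.
- *Safeguards exist.* The sponsor must be consulted on the increase. Section 4.1.4.1 has the investigator obtain sponsor confirmation of the dose before each new course, and Appendix 10.4 refers questions to the sponsor. These reduce the risk, but they leave the sponsor applying the same conflicting text.
- *Ritonavir.* The table permits dual listing. Section 1.2 does not say how long ritonavir was given, so it cannot show that the inducer entry is wrong. Known HIV carriers are excluded, so use is presumably rare. All of this stands; the missing rule for a dual-listed drug also stands.
- *Analysis.* The SAP already plans treatment time by dose level (Section 7.7) and a description of concomitant medication (Section 7.2). Response is analysed in all treated patients. Tables of response with and without affected patients would be a matter of preference, and they are not requested here.

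**Conclusion.** The point holds as a conflict between instructions. It affects three small groups: dose-reduced patients who later need a strong inducer; patients on ritonavir; and, for deviation coding only, expansion patients whose dose is raised because of an inducer. As tabulated, C1 excludes nobody, so the set for the primary response analysis does not change. What can be affected is individual patient management, the consistency of deviation coding, and the reading of safety by dose.

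Two stronger inferences are tempting but unsupported. First, a reader might conclude that expansion patients on inducers would be treated above the MTD and so contaminate data labelled as MTD. Only the nominal dose would exceed level 0. With a rifampicin-size effect and a one-tier increase, exposure would be about 0.83 to 0.84 of that at level 0 without an inducer, assuming dose-proportionality; the protocol gives no interaction figure for the antiepileptics. Second, because three of the four main cohorts are brain tumours and the inducer list includes carbamazepine, phenytoin and phenobarbital, a reader might expect inducer use to be common. The documents give no frequency of seizures or antiepileptic use in this population, and Section 4.2.3.1 asks that P-gp modulators be avoided before the first dose. Any statement about frequency is an assumption.

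**What to change.** The sponsor should:

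1. Reconcile Section 4.2.3.1 and Appendix 10.4 with Section 4.1.4.3, so that a dose-reduced patient who needs an inducer falls under one instruction.
2. State how the inducer instruction relates to footnote 15 and Section 4.1.4.2, so that C1 can be coded consistently.
3. Reconcile the double listing of ritonavir in Table 10.4:1 with Sections 1.2 and 4.2.3.1, and say which instruction applies to a drug listed in both columns.

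Which clinical rule should prevail is for the sponsor and its clinical advisers; none is proposed here. As an option, the SAP could add a listing of expansion patients whose nominal dose exceeded level 0 because of an inducer.

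The cost is a few sentences of protocol text and, if adopted, one flag. Concomitant therapy is already recorded, and treatment time is already to be summarised by dose level, so no new data collection should be needed.

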4.2.3.2 Restrictions on diet and life style

Patients should be advised to avoid any foods known to aggravate diarrhoea.

To prevent skin related adverse events it is recommended to avoid intense irradiation with UV light and harsh detergents, see also [Section 4.2.2.2](#).

